Due to randomization, we cannot schedule the group time and date before the participant enrolls in the study. Thus, it is likely that many participants will be randomized into a group that is being held during a time when they are no available. Thus, we will offer, as a courtesy, The opportunity for people who are enrolled in the study to participate in a full intervention group after they complete their participation in the study. These groups will be provided by the licensed facilitator and it will not be a part of the study. No data will be collected and this will be offered solely to give participants the option to engage in the intervention.

11. EQUIPMENT Will any physical stimulation or physiological data acquisition equipment be used with the subjects?

Yes No If yes, attach **Appendix A**, the *Research Equipment Form*.

12. DEVICES Will any devices be used with the subjects?

Yes No If yes, attach **Appendix B-1**.

13. DRUGS AND BIOLOGICS Will any drugs or chemical or biological agents be used with the subjects?

Yes No If yes, attach **Appendix B-2**.

14. MRI AT BIC To use the Beckman Institute Biomedical Imaging Center (BIC) in human subject's research, you must obtain *prior approval* from the BIC [contact]; [contact]) and use BIC-approved screening and consent forms. Attach:

BIC approval Attached
BIC screening form Attached
BIC consent form Attached

15. MEASURES If subjects will complete questionnaires, surveys, interviews, psychological measures, or other measures, however administered, the IRB must review and approve the measures. List all such measures here and attach complete, labeled copies (including translations, if applicable) to this application:

CLINICAL SCREEN  Attached	
Measure 1:	Mini Mental
Measure 2:	Mini suicidality screen
Measure 3:	Mini Psychotic Assessment
Measure 4:	GAIN
BASELINE  Attached	
Measure 5:	Demographics
Measure 6:	Timeline Follow-back
Measure 7:	Crime and violence scale (part of GAIN)
Measure 8:	States of Engaged Awareness about Health Inequalities(developed by us)
FOLLOW-UP  Attached	
Measure 9:	Demographics
Measure 10:	Timeline Follow-back
Measure 11:	Crime and violence scale

Measure 12:	States of Engaged Awareness about Health Inequalities (developed by us)
Measure 13:	Treatment Services Review (TSR)
Measure 14:	Yalom Group Scale
Measure 15:	Use of Treatment Skills (UTS- developed by use)
Measure 16:	End of treatment questionnaire (ETQ- Developed by us)

List additional Measures on an attachment and check here:

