 Outpatients	 Other College Students—name subject _____
 Elderly (age > 65)	
 Other (describe here): _____	

7F. If you checked any of the groups in question 7E, describe additional safeguards included in the protocol to protect the rights and welfare of special or vulnerable populations.

To avoid possible violations of confidentiality, project staff are trained to carefully follow detailed procedures designed to assure that no information about any participant (or others they may mention) will be given to law enforcement, other government agencies, or anyone but research staff. Every member of the research team and all Newark Community Collaborative Board (NCCB) members will be required to undergo human subject protection training and provide a certificate of completion to the IRB prior to any contact with human subjects. Standards of confidentiality include the use of code numbers and code names for participants and other individuals they may mention. The only place participants' names or other identifying information will appear is on informed consent forms and locator forms (used for follow-up interviews after the baseline). These forms will be kept electronically in box, in a folder separate from the data. Only full time, trained staff in the project including the outreach works, group facilitators, PD and PIs will have access to these files. Peer facilitator and licensed facilitator will not have access to data from the individuals that are randomized into their groups.

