10. RESEARCH PROCEDURES: Using LAYMAN'S LANGUAGE, specifically describe what the participants (treatment groups and controls) will do and where the research activities will take place. Give approximate dates and durations for specific activities, including the total number of treatments, visits, or meetings required and the total time commitment.

(For schools-based research where class time is used, describe in detail the activities planned for nonparticipants and explain where (e.g., in a classroom, in a private area) both participants and nonparticipants will be located during the research activities. Include a concise description of procedures, locations, time commitments, and alternate activities on the relevant consent and assent forms.)

All research activities will take place at NJCRI. Drug screening will take place at baseline and follow-up assessments conducted by trained full time staff supervised by the project director. Participants will be told by the RA that they have a right to refuse to complete the drug screen and that results will not be shared with staff at NJCRI. Results will be used to enhance the rigor of the study as an added source of information about drug use.

Intervention groups will be held at NJCRI. The research team is being hired through NJCRI and will have offices in the building. [name] and [name] will be the contact people at NJCRI. NJCRI will provide the research team with an office space for each project full time employee (project director, outreach worker, and group facilitators) in addition to conference rooms where the research groups will take place.

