The project applies community based participatory research (CBPR) principles to the multiphase optimization strategy (MOST) framework in implementing a 2x2x2 factorial design in which 592 men with substance use disorders and a history of incarceration residing in Essex County, NJ will be randomized into one of sixteen conditions: 1) Critical Dialogue (CD) only, facilitated by a licensed facilitator (LF). 2) Critical Dialogue (CD) only, facilitated by a peer facilitator (PF). 3) Quality-of-Life-Wheel (QLW) only, facilitated by LF. 4) Quality of Life Wheel only, facilitated by PF. 5) Capacity building project (CBP) only, facilitated by LF. 6) CBP only, facilitated by PF. 7) CD+QLW facilitated by LF. 8) CD+QLW facilitated by PF. 9) CD+CBP facilitated by LF. 10) CD+CBP facilitated by PF. 11) QLW+CBP facilitated by LF. 12) QLW+CBP facilitated by PF. 13) CD+QLW+CBP facilitated by LF. 14) CD+QLW+CBP facilitated by PF. 15) Core Component facilitated by LF and 16) Core Component facilitated by PF. All groups will receive the core component of the intervention which includes introduction, critical thinking session and graduation.

Facilitators, whether licensed or peer, may or may not be members of the NCCB. In the event a NCCB member is selected to be a group facilitator, they will not have access to any of the research data collected in the groups they are facilitating and they will need to leave any portion of the NCCB meetings where we may discuss their groups. This will be done to avoid bias in the group facilitation and in the data.

Core component includes an introduction session, a critical thinking session, and the graduation. This is designed to give participants tools to assess their own thinking and hence, their assumptions that may contribute to substance use;

Critical Dialogue consists of group conversations prompted by thematic images. It aims to help participants develop a deeper understanding of how marginalizing processes (e.g., systematic stigma; feelings of rage as victims of discrimination) impact their lives and behavior;

Quality-of-Life-Wheel consists of individual and group exercises to develop individual goals. It aims to increase self-efficacy and help participants develop a vision for their future, breaking this vision down into small, feasible, measureable goals they can implement on a weekly basis (e.g. quitting smoking, improving relationships with family members, paying down debt);

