Capacity Building Projects consist of projects created by the groups to address a community problem. The capacity building projects are designed to create collaborative efforts to overcome and dismantle marginalizing processes by building positive social and organizational relationships and community capacity through the development and implementation of community projects aiming to address social determinants of health.

Facilitation by both licensed clinician and peer facilitator will provide an opportunity to test not only the efficacy of delivering the intervention through peers but will also determine the cost effectiveness of peer delivery vs. licensed facilitators.

Prior to the being consented into the study at baseline, participants will have the opportunity to attend an orientation session where we will explain the research design, the different conditions available, the randomization process, and the risks and benefits of participation in the study. We will emphasize the difference between the intervention and the research (mainly group sessions and data collection sessions). We hope that this make the participants better informed about the study and minimize contamination by explaining the importance to keep their activities in each group private. Data will be collected in six waves and will include a baseline and five monthly follow-up interviews. These interventions were developed and pilot tested by our team. We will also randomly select 24 groups to participate in focus groups and provide their feedback about their experience participating in the intervention. We will randomly select one group per intervention condition and only participants who attended at least one intervention session will be eligible to participate. We will keep track of other services that participants seek during follow-up assessments and we will control for the impact of these services statistically.

Below is a table displaying research activities. Note that for follow-up, depending on which condition someone is randomized into, they may complete between 1 to 5 follow-ups post intervention, receiving \$20 per follow-up plus \$2.50 for each intervention session they attend. This occurs because of the variance in the number in intervention sessions among the different conditions.:

Activity	Cost per participant	Time	Professional Assigned
Clinical screens	\$10	30 minutes	Licensed NCCB clinicians
Baselines	\$20	90 minutes	

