Facilitators complete a checklist at the end of each *Community Wise* group session to list the activities completed and group attendance. Facilitators will upload the checklists directly to a facilitator-assigned folder in Box, the study's secured server, where they will be reviewed by the PIs and the PD.

Participants will use both codenames and code numbers, which will be connected in the electronic key list, but not in the database. We use this strategy to facilitate (and humanize) participants as we talk about them in meetings (including clinical supervision, NCCB meetings, and in *Community Wise* groups). Participants can request that we destroy their data (except group voice recordings) at any time until data collection is completed by notifying one of the PIs by phone or e-mail. After that we will destroy the electronic key and we will be unable to determine what data belongs to whom. Note that voice recordings will be kept indefinitely.

The clinical screen will be an in-person interview conducted by the study local PI, the licensed facilitator, or the project director who will be properly trained by [name].

Urine screens will be collected in person by a trained staff person. Baseline and follow-up will be administered through Redcap on the laptop during the small group sessions and administered by trained full time staff. The peer facilitator will only be allowed to collect data from participants in the licensed facilitator groups and vice versa.

Focus groups will be facilitated in person by the local PI or trained staff members who did not facilitate the group being interviewed.

NCCB members and project staff will recuse themselves from interacting with anyone they personally know as a part of study activities. We will have study interviewers review the name of the person they are interviewing prior to the interview to make sure they do not personally know them. If they do, we will find someone else to conduct the interview. If a NCCB member unexpectedly encounters someone they know at a study related activity, they will recuse themselves and notify the project director and the principal investigators. The project director will keep a list of participants that we identify as having a personal relationship with NCCB members or staff and we will make sure these individuals are not booked together for any study related activities.

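### Facilitators may collect data only in the opposite facilitator arm, so any visit they collect ties assessor type to the licensed-versus-peer factor; the plan should name one independent collector

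*Combined protocol and SAP*

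**What the plan says.** **The rule.** Section 10 (Research Procedures) states: "The peer facilitator will only be allowed to collect data from participants in the licensed facilitator groups and vice versa". The preceding sentence has baseline and follow-up "administered by trained full time staff".

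**Why the factor matters.** Section 10 says that using both facilitator types lets the study "test not only the efficacy of delivering the intervention through peers" and compare cost-effectiveness. Facilitator type splits the sixteen conditions in half.

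**Who collects.** The text gives several answers:

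- Section 10, opening: "Drug screening will take place at baseline and follow-up assessments conducted by trained full time staff supervised by the project director".
- Section 10, same part, listing full-time employees: "office space for each project full time employee (project director, outreach worker, and group facilitators". Research assistants are not in that list.
- Section 7F, on access to identifying files: "full time, trained staff in the project including the outreach works, group facilitators, PD and PIs".
- Section 10, Measures: a research assistant schedules and runs sittings of up to eight men, reads the urine test and pays the participants.
- Section 10, activity table: community board members and research assistants for follow-ups. The table is broken in the extracted text, so this is weak evidence.
- Section 18B: an assistant staff member.
- Incentive and Study Activities sheets: a research assistant for baseline and all five follow-ups, in every condition.

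**Related safeguards.** Section 7F says "Peer facilitator and licensed facilitator will not have access to data from the individuals that are randomized into their groups". Section 10 says of board members who facilitate that "they will not have access to any of the research data collected in the groups they are facilitating". Both concern access to data. Section 20A separately bars facilitators from collecting data in their own groups.

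**The concern.** Keeping facilitators away from their own groups' assessments is sound. The Section 10 rule is worded by facilitator type, however. When a facilitator collects, a man in a licensed-facilitator group is always assessed by a peer, and a man in a peer group always by a licensed clinician. If men report substance use differently to a peer than to a clinician, that difference enters the licensed-versus-peer contrast and looks like an effect of who delivered the intervention.

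Within facilitator-collected visits no model can separate the two. Only visits collected by someone else carry clean information on the contrast. The text available states neither the share of visits facilitators would collect nor an adjustment for assessor, and a site reading it could not tell who is meant to collect the outcome data.

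**Working it through.** The available text gives no power, alpha or assessor figure for the facilitator contrast, so there is no plan figure to reproduce. The check has three parts.

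**1. Is the tie complete where it applies?** Code the sixteen conditions as a 2×2×2×2 design (Critical Dialogue, Quality-of-Life Wheel, Capacity Building Project, facilitator) and set assessor type by the Section 10 rule.

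- Correlation of assessor type with facilitator type: −1.
- Correlation with each of the three content components: 0.
- Intercept, four main effects and assessor type form 6 columns of rank 5.

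Assessor and facilitator type are fully aliased in facilitator-collected visits. The three component main effects are not aliased with assessor type.

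**2. Can such visits arise?** The two readings, side by side:

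- *Yes.* Full-time staff administer baseline, follow-up and the urine screen (Section 10), and full-time staff include facilitators (Sections 7F and 10). The rule itself would have little purpose if facilitators never collected.
- *No.* The step-by-step account under Measures and all eight Incentive and Study Activities sheets name a research assistant. The full-time list also contains the project director and outreach worker, so the full-time wording can be met without facilitators.

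The text does not settle it.

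**3. How large could the effect be?** Let *p* be the share of visits collected by facilitators. Let the shifts in recorded outcome, relative to a research assistant, be a_L for a licensed assessor and a_P for a peer assessor. Then

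bias (peer arm minus licensed arm) = p(peer arm) × a_L − p(licensed arm) × a_P.

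With the same *p* in both arms this is p × d, where d = a_L − a_P.

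Inputs from the documents: 592 men, hence 592/2 = 296 per level under equal allocation; groups of up to 11 (Section 18B). Assumptions: ICC 0.05, no true facilitator effect, two-sided alpha 0.05, one visit, *p* equal in both arms, and all values of *p* and *d*.

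- SE without clustering = √(2/296) = 0.0822 SD.
- Design effect = 1 + (11 − 1) × 0.05 = 1.5.
- SE with clustering = 0.0822 × √1.5 = 0.1007 SD.
- Type I error = P(|Z| > 1.96) for Z normal with mean p × d / SE and variance 1.

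| d (SD) | p | bias p × d (SD) | type I error |
|---|---|---|---|
| any | 0 | 0 | 0.050 |
| 0.1 | 0.10 | 0.010 | 0.051 |
| 0.1 | 0.25 | 0.025 | 0.057 |
| 0.1 | 0.50 | 0.050 | 0.079 |
| 0.2 | 0.10 | 0.020 | 0.055 |
| 0.2 | 0.25 | 0.050 | 0.079 |
| 0.2 | 0.50 | 0.100 | 0.168 |

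Example: at d = 0.2 and p = 0.50, the mean is 0.100/0.1007 = 0.993 and the two tails sum to 0.168. Without clustering the last three rows become 0.057, 0.093 and 0.229.

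Error reaches 0.10 when p × d is about 0.066 SD: a 33% share at d = 0.2, or 66% at d = 0.1. For scale, the difference detectable with 80% power under the same SE is 2.80 × 0.1007 = 0.28 SD.

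**The case against.** The strongest reply is that the problem may never occur. The rule limits who may collect; it does not assign anyone. The most detailed operational text names a research assistant throughout, and then the bias is exactly zero. This stands, and it is why the point is conditional.

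Second, any assessor difference is likely to be small. Section 18B has each man complete the survey alone on a tablet, and the urine result is read from a rapid test. This also stands in large part. It does not remove the assessor altogether: Section 18B also lists face-to-face computer-assisted interviews, and the collector answers questions and handles the sample.

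Third, Section 18B places randomization before baseline is scheduled. The rule could then apply at baseline too, and a stable assessor shift would partly cancel in a baseline-adjusted analysis. The one-visit illustration ignores this, so it may overstate the effect.

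A reader might also draw stronger conclusions that the documents do not support:

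- *That the whole licensed-versus-peer contrast is confounded.* Only facilitator-collected visits are tied, and their share is unstated.
- *That the rule is plainly wider than the own-group bar in Section 20A.* Section 10 speaks of the licensed facilitator in the singular. If one of each type is active, the two rules coincide.
- *That facilitator cover could simply be balanced across arms.* With one active licensed facilitator this is impossible without own-group assessment. The four peers in Section 18D are hired so that a replacement is available, which does not show that several run groups in parallel.
- *That nothing can be checked later because no collector is recorded at follow-up.* The tracking-sheet headers are partly absent or scrambled in the extracted text, so that absence proves nothing.

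**Conclusion.** The point holds in a limited form. Where a facilitator collects, assessor type is fully aliased with a randomized factor that the study sets out to test. Whether facilitators will collect cannot be determined, because the protocol names different collectors in different places. That inconsistency is certain; the bias is conditional.

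Its size is the facilitator-collected share times the assessor difference, given equal shares in both arms. Neither quantity is in the documents. At an assumed 0.2 SD difference, type I error for this one contrast is about 0.08 at a 25% share and 0.17 at 50%; at 0.1 SD it stays at or below about 0.08 up to a 50% share. These figures rest on the stated ICC, single-visit and no-true-effect assumptions and are illustrations only. The main effects of Critical Dialogue, Quality-of-Life Wheel and Capacity Building Project are unaffected if the share is equal across component conditions.

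This is a cheap improvement worth making. It is not evidence that the facilitator comparison is invalid. Confidence is medium.

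**What to change.** 1. Reconcile the statements on who collects outcomes: the drug-screening, staffing, activity-table, Measures and administration text in Section 10, the data-collection text in Section 18B, and the Incentive and Study Activities sheets.
2. Replace the facilitator sentence in Section 10 with: *Research assistants who do not facilitate groups collect baseline and follow-up outcomes, including the urine screen, in all conditions; facilitators do not collect outcome data.*
3. Record collector role in REDCap at every visit, baseline and follow-up.
4. If any facilitator-collected visits occur, report their share by facilitator arm and add one prespecified sensitivity analysis of the licensed-versus-peer contrast that excludes them. Collector may be set after randomization, so this analysis is supportive only. It also costs precision: under the assumptions above, the SE rises from 0.1007 to about 0.1007/√0.75 = 0.116 at a 25% share.

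**Cost.** One sentence and one data field. If the Incentive and Study Activities sheets already govern, there is no added workload. If full-time staff were meant to collect, research assistants take on more sittings and scheduling is less flexible. At up to eight men per sitting, 592 × 6 = 3,552 visits need at least 3,552/8 = 444 sittings; a 25% facilitator share would shift at least 111 of them. Hours are not estimated, because the stated follow-up length differs between Section 10 (90 minutes) and most of the sheets (60 minutes).

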16. SUBJECT REMUNERATION

Will subjects receive inducements or rewards before, during, or after participation? Yes

No

If yes, will payment be prorated for partial participation? Yes

No

If remuneration will be given, for each subject group:

- (1) specify the form of remuneration, including \$, course credit, lottery, gift certificate, or other;
- (2) state the \$ amount or the approximate \$US value, or the course credit and its percentage of the final grade;
- (3) explain the remuneration plan, including whether and how prorating will be made for partial participation;
- (4) for lotteries, include (a) the number of prizes, (b) the nature and value of each prize, (c) the approximate odds of winning, (d) the date(s) of the drawing(s), and (e) how winners will be notified, by whom, and by when; and
- (5) include all this information on the relevant consent forms.

Incentives will be distributed in cash at the completion of each study tasks described in the table above. Participants may earn as much as \$187.5 over 5 months if they complete all study activities. For instance, someone randomized into condition 14 (full intervention) who completes all study activities will receive: \$10 for clinical screen, \$20 for baseline, \$20 for the all follow-ups plus \$10 for each of the first 3 follow-ups for attending 4 intervention sessions per month, \$7.50 for attending 3 intervention sessions in follow up 4 \$20 for focus group if they are randomized to complete the focus group = \$187.5. Someone randomized to receive condition 15 (core component only) and randomized not to complete the focus group who completes all study activities will receive \$10 for clinical screen, \$20 for baseline, \$20 for each follow-up, in addition to \$7.50 for follow-up 1 only will earn \$137.50 over the course of the study.

NCCB members will receive \$20 per hour worked, generally in meetings of 2 hours each. They will also receive \$100 per 4 hour long retreat they attend. NCCB retreats are, for the most part, long NCCB meetings. Retreats can be more informal and build in opportunities for members to simply engage with one another, bring family and friends, and increase our bond. No confidential materials are discussed during open session retreats where non-NCCB members are present. If there is an agenda of items we need to discuss more formally, we use the same exact procedures as those described for meetings and collect the same data (video recording of the meeting). NCCB members

may also receive compensation for referring participants to the Community Wise randomized controlled trial. They will receive \$5 per enrolled participant they refer. NCCB members will not know the identity of those they referred who successfully enrolled. Participants will contact the outreach worker directly and during the phone screen, we will ask them who referred them to the study. Those NCCB members who are named by the enrolled participants will receive a lump sum once recruitment is ended.

17. SUBJECT OUTLAY Will subjects incur costs for research-related procedures (e.g., longer hospitalization, extra tests), use of equipment, lost compensation, or transportation (over 50 miles)?
 Yes No If yes, describe here:

18. CONFIDENTIALITY OF DATA Answer each of the following to describe methods that will ensure the confidentiality of individually identifiable data. Confidentiality is required unless subjects give express, written permission to have their identifiable information published, presented, or shared.

18A. CHECK IF USED IN DATA COLLECTION: Audio tapes/ Video tapes Still photos Other imaging
Digital voice

18B. DATA COLLECTION Explain how the data will be collected. If anonymous data collection is proposed, provide details of how investigators *will not have the ability to trace responses to subject identities*. For multiphase data collection or if multiple contacts will be made with subjects, specifically explain the subject tracking and coding systems.

Address the confidentiality of data collected via e-mail, databases, Web interfaces, computer servers, and other networked information, as applicable.

Data will be generated and collected through face-to-face computer assisted interviews, computer assisted self-interviews, focus groups, and group session audio recordings. This will include brief telephone screenings, clinical screenings, baseline, five post baseline follow-ups, focus groups and intervention sessions. Interested individuals will call the study's confidential phone number and complete a brief telephone screen with a research assistant who will obtain self-reported identifying and eligibility information such as birth date, complete name, last incarceration date and place, gender, current AIDU, and whether they reside in Essex County, NJ. Before completing the phone screen, participants will be given a brief description of the study and they will be informed that the information they release on the phone will be kept confidential and will be used only to verify eligibility (including verification of their last incarceration place and date based on public records). This information will be kept in a password secured Excel file in a password secured laptop at a

locked office at NJCRI. Those found to be eligible will be invited to complete the clinical screen with a licensed clinician at NJCRI. Prior to completing the clinical screen, participants will learn more about the study and the clinical screen. They will sign an informed consent to participate in the clinical screen which will include Mini Mental State Exam, MINI International Neuropsychiatric Interview 6 psychoticism and suicidality modules, and the Global Appraisal of Individual Needs-Substance Problem Scale (GAIN-SPS). Those found to be eligible will learn about the randomization process and the study procedures. The clinician will go through the informed consent and those who agree will be randomized into one of eight experimental conditions and we will schedule the baseline. Participants may take the informed consent with them and think about whether to participate or not, as long as we are still recruiting. Paper data will be kept at a locked file cabinet at NJCRI. A code number and a codename will be assigned to each participant completing the clinical screen and only this code number and codename will be used in the paper and electronic data collection. A master list will be created linking names with code numbers and this list will be kept in a password protected excel file in the PD's computer in a locked office at NJCRI.

Baseline and follow-up data will be collected at NJCRI by assistant staff member. *Community Wise* group participants will be scheduled to complete the data collection on the same day and time. Each participant will work independently on a private tablet using RedCap data collection management software. We will collect outcome, process, and safety monitoring measures (e.g. MINI suicidality) including AIDU, use of treatment skills measure, and their perceptions about helpful components. This electronic data will only contain the code numbers and codenames and it will be stored in a secured server at the University of Illinois at Urbana Champaign. Data will be securely uploaded into the server immediately after data collection. Only authorized personnel will have access to it.

During the baseline assessment, we will ask participants permission to take a digital photograph of them during the baseline to assist with finding them during follow-ups. The photo of those who consent will be taken by the RA and immediately uploaded into the master file along with the name and identifying information, but not linked to any data. Photographs will be used by the outreach workers to recognize participants on the streets and they will be destroyed as soon as the participant completes follow up 5. Participants will have the option to refuse without penalty and they may ask us to destroy their photo at any time during the study.

No research will be conducted with any subject while they are incarcerated.

Focus groups

Sixteen out of 48 *Community Wise* groups of up to eleven participants each will be randomly selected in advance during year 1 to be included in the focus groups throughout the six waves. Participants from selected groups who attended at least one *Community Wise* session will be invited to attend the focus group at the end of each data collection wave. The focus groups will be conducted at NJCRI by a trained RA, and will be audio-recorded and transcribed for analysis. Focus group sessions will be structured and the RA will be trained to keep the discussion focused on clients' satisfaction with the intervention. If a participant starts to talk about personal issues, the RA will stop them and offer to refer them to talk to an Integrity House counselor if appropriate (see focus group script). Data will be uploaded into a password-secured server at the University of Illinois at Urbana-Champaign. Only code numbers will be included with the electronic data.

Audio Recordings

All *Community Wise* sessions will be voice-recorded for the purposes of treatment fidelity and quality control. Agreement to be voice-recorded is a requirement for eligibility and it will be fully explained

during the informed consent process. Session audio files will be kept in a password secured server at the University of Illinois at Urbana-Champaign. The files will be accessed only by and the PIs, the PD, and research assistants who will listen to randomly selected sessions to complete the treatment fidelity and participant safety measures. These measures will only include code numbers and they will be stored in the server at the University of Illinois where the data analysis will take place.

NCCB meetings

The NCCB is a diverse community collaborative board of up to 20 community residents, consumers, researchers, service providers and government representatives working together to build a safer and healthier city through the implementation of a comprehensive community based health program that fosters advocacy of health and community reentry issues at the government level. Over the past 5 years, the NCCB has developed and pilot tested *Community Wise*. The NCCB will meet as a full board 6 times each year for 2 hours each time, to monitor the current research progress including training, recruitment, data collection, services delivery, data analysis, and dissemination. Members will also meet in committees, to work on specific aspects of the study (e.g., revising manuals, developing capacity building projects). Only NCCB members who are not listed in the current research budget will be compensated for attending meetings (\$20 per hour). NCCB meetings will be video recorded so that detailed minutes can be taken and the research team can collect data on how decisions were made among NCCB members. Detailed meeting minutes are taken and approved each meeting. Videos are available at a private Blackboard virtual collaboration site to be reviewed by any NCCB member. Each NCCB member has a password and login ID to access the collaboration site. NCCB members will also participate in annual evaluations of the NCCB and its chair, which will be overseen by [name], the project's co-investigator. [name] is at the University of Michigan and he is responsible for evaluating our adherence to CBPR principles and the quality of communication and satisfaction among NCCB members. Anonymous evaluation data will be collected via Qualtrix and only [name] will have access to it. Results will be used to gage the health of collaboration within the NCCB and the application of CBPR principles. Participation will be voluntary.

We will use a REDCap to track participants' progress throughout the project. We will keep one password protected file that will contain participants' names, phone number, e-mail address, residence address, Facebook page, permission to contact them, and specific instructions about what type of message we may or may not leave. We will also collect information about friends and family members that we may contact if we lose communication with participants.

We will find out about participants being incarcerated in one of three ways: 1) someone tells us about it while we are attempting to contact the person, 2) the person themselves find a way to notify us, 3) we run a public search for incarceration in state and federal websites. Once we find someone who was incarcerated, we will check to see if they granted authorization for us to pursue them. If authorization was given, we will find out who is the appropriate authority and we will call them to make a formal request to visit the participant. We will simply state that the person is a participant in a health research study and that we would like to schedule a time to collect the follow up data in the facility. We will explain that the data will be collected using the REDCap and that once it is submitted by the participants in the tablet, it is encrypted. The data is completely confidential and protected by the COC. We will only schedule the interview if the responsible official grants us permission and agrees to provide us with a private room (incarceration officers can see us, but not hear us) for up to 1.5 hours, and agrees that the data collected will be confidential. The tablet does not have internet connection and it will not have any other programs or information installed outside of the Redcap interview. We will not conduct the urine drug screen as that is not safe or feasible in an incarceration setting. These interviews will be conducted personally by the local PI or the PD.

18C. DATA SECURITY Describe how and where the data be kept so that the data remain confidential.

We will use the same strategy we developed during our pilot study to store hard paper data, including informed consent forms, papers completed during the clinical screen, and incentive receipts. This data will be organized into separate folders and locked into file cabinets that will be in the project director's locked office. Forms containing identifying information will not contain either the codename or the code numbers and they will be stored separately from the data. All paper forms will be kept for at least 3 years after study completion.

Electronic files containing identifying information will be stored in Box . A master list will be created linking code numbers to identifying information. Only fulltime staff will have access to participants identifying information. Participants will have the choice to use their real names in the group or request that they only use their codenames. This information will be deleted at study completion (once analysis is complete).

Facilitators will have contact information for the participants so that they can contact them to schedule/cancel meetings/ data collection, and check in during the week if needed. This information will be kept in the facilitator's password protected study cell phone and will include instructions on whether it is all right to leave a message and under what circumstance for each participant.

All de-identified electronic data, including NCCB videos and focus group and Community Wise session group voice recordings will be stored in a Box cloud contracted through the University of Illinois (see <https://www.box.com/business/>). Folders for specific content will be created and permissions will be assigned accordingly to members of the NCCB who are assigned to work with specific data files. The PIs and the project director will have access to all files. Other team members will gain access based on the tasks they are assigned and cleared to complete. All team members will receive training on each task they are to perform by the PIs or the PD and they will not receive access to data until they have been cleared by one of the PIs or the PD. [name] will be responsible for tracking who has access to what at any given time. This data will be kept indefinitely for the purposes of data analysis.

